6.2.4 PREPARATION

Study intervention will be prepared on site consistent with local policies and procedures and started within 36 hours of randomization. The administration of each unit will be performed by qualified individuals, in a blinded fashion.

Detailed information about proper preparation and blinding procedures can be found in the Drug Treatment & Handling Procedures (DTHP).

6.3 MEASURES TO MINIMIZE BIAS: RANDOMIZATION AND BLINDING

6.3.1 RANDOMIZATION

The study will randomize participants in equal probabilities to study treatment arms. Currently there are two study treatment arms: convalescent plasma versus saline. Participants will be randomized in 1:1 ratio to these two arms. If additional arms are added to or dropped from the trial, randomization will proceed with an equal probability to each of the remaining arms. Randomization will be stratified by participating site and by age (≥ 65 vs. < 65 years old).

The IWRS (Interactive Web Response System) will be used by authorized study site personnel to randomize eligible participants. It is an intranet-based application that is hosted behind the VA firewall on a VA server at the CSPCRPCC. It is only accessible on the VA network to authenticated VA personnel. Access to study data is restricted to personnel that have registered in the IWRS and have been authorized by the study team. All communication to or from the IWRS is encrypted using Hypertext Transfer Protocol Secure (HTTPS) and is secured using a VA furnished Secure Sockets Layer (SSL) certificate.

6.3.2 BLINDING

The study interventions will be provided and administered to all participants in a similar fashion to achieve blinding. The participants, site investigators, clinical prescribers, site coordinators, and most other individuals involved in this study will be blinded to the treatment assignment. Furthermore, the blind will not routinely be broken in order to select post-study, pharmacologic treatment for SARS-CoV-2 infection administered by clinical healthcare providers.

Blinding will be maintained except for when knowledge of the study treatment assignment will influence the medical treatment of the participant. There may be cases of breaking the blind for emergency medical necessity (emergency unmasking), where the clinical research pharmacist may access treatment assignment information, as necessary. If emergency unblinding becomes necessary during local business hours, the treating provider should contact the Local Site Investigator. The LSI should then contact the Study Chair to discuss the situation before requesting that a participant be unblinded by the CSPCRPCC. Outside of local business hours, the treating provider should contact CSPCRPCC directly at a number that is available 24 hours per day, 7 days per week to discuss the need for unblinding and to have the unblinding performed if indicated. Efforts should be made to avoid unblinding unless medically necessary for emergency treatment decisions.

Participants who require emergency unblinding for clinical safety will be discontinued from study intervention. Study staff will be provided with training on emergency unblinding procedures.

Participants or their legally authorized representative will be provided with a Participant Identification Card that lists site staff telephone numbers and a 24-hour CSPCRPCC contact number. The research facility's name and the two possible study treatments are also listed on the card. The Participant Identification Card will include the participant's Randomization Number, which can be used to determine the participant's treatment assignment should emergency unblinding be required for patient safety.

6.4 STUDY INTERVENTION COMPLIANCE

The study intervention consists of intravenous administration of 200-600mL of convalescent plasma or an equivalent volume of 0.9% saline administered in two equally divided doses, less than 12 hours apart. The order will be entered by the site LSI or authorized designee and study product will be administered by clinical staff according to standard procedures for transfusion of component blood products.

Compliance with study intervention will be assessed using case report forms entered by local site staff following completed transfusion of study intervention.

The reason for failure or partial administration of study product will be recorded by study staff.

6.5 CONCOMITANT THERAPY

Therapy prior to enrollment with any other experimental treatment or off-label use of marketed medications that are intended as specific treatment for SARS-CoV-2 infection (i.e., post-exposure prophylaxis) are permitted.

Participants who are taking remdesivir for COVID-19 or another antiviral for a concurrent infection (e.g. oseltamivir for an influenza virus, lopinavir/ritonavir for HIV, etc.), or

immunosuppressive drugs for other medical conditions (corticosteroids for an unrelated condition, tocilizumab for rheumatoid arthritis, hydroxychloroquine for lupus, etc.) may continue with the treatment.

Participants entering the trial may be prescribed therapy for SARS-CoV-2 that has received preliminary FDA approval whether available by prescription or under an expanded access program (EAP), e.g. remdesivir or dexamethasone. These medications may be initiated or continued. However, participants may not have previously received or be given SARS-CoV-2 convalescent plasma under the Mayo or any other EAP.

A participant cannot participate in another clinical trial for the treatment of SARS-CoV-2 until after Day 29. However, if the participant has progressed to respiratory failure in the hospital (see definition in *Section 3*), another experimental treatment protocol may be initiated, but only if there is a sponsor-approved agreement between the leadership of both trials. The agreement will consider potential impact of dual enrollment on study outcomes and participant safety and establish procedures to coordinate adverse event monitoring and reporting of dual-enrolled participants.

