2 INTRODUCTION

2.1 STUDY RATIONALE

Since December 2019, SARS-CoV-2 (SARS-CoV-2; COVID-19) infections are over 6 million persons and approaching 200,000 deaths in the US with a continually rising rate of infection. Of the ≈20% of patients admitted to hospital, up to half progress to ICU admission, respiratory failure or death. Prominent among these progressors are older men, particularly those with underlying comorbidities (e.g., hypertension, diabetes, lung, heart, kidney or liver disease, obesity and immunocompromised)¹, all common among Veterans. Effective interventions are few, other than recently-approved remdesivir, which shortened hospital stay but did not decrease overall mortality¹⁶. Convalescent plasma from persons recovered from SARS-CoV-2 infection is readily available for treatment.

Convalescent plasma therapy is being used empirically, although only five of six small uncontrolled case series (total n=56) in SARS-CoV-2³⁻⁸ and a recent study with non-randomized controls⁹ suggest improved selected clinical, virologic and laboratory outcomes and outcomes in another small randomized trial were equivocal¹⁷. For other infections, such as influenza and Ebola virus, promising observational studies were not reliably confirmed by controlled trials^{10,11-15}. In multiple infections, use of convalescent plasma has been distinguished by its safety profile but not by the consistency of its benefit. The current double-blind, placebo-controlled RCT is designed to determine definitively whether this intervention is effective in a population at high risk of complications and death from SARS-CoV-2 infection. We compare the effect of convalescent plasma vs. saline placebo with a robust study design, adequate sample size and statistical and logistical rigor to assure that the interventions we make to treat serious disease are well-validated to support its use or to move on to test other potentially safe and effective treatments.

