5 STUDY POPULATION

5.1 INCLUSION CRITERIA

Veterans must meet ALL of the following criteria to be eligible to participate:

1. Admitted to a participating VA clinical site with symptoms suggestive of SARS-CoV-2 infection.
2. Participant (or legally authorized representative) provides informed consent prior to initiation of any study procedures.
3. Participant (or legally authorized representative) understands and agrees to comply with planned study procedures.
4. Veteran \geq 18 years of age at time of screening.
5. Has laboratory-confirmed SARS-CoV-2 infection as determined by polymerase chain reaction (PCR) or antigen test, as documented by either of the following:
 - (1) RT-PCR or antigen positive (nasopharyngeal, oropharyngeal, saliva, lower respiratory) in sample collected \leq 72 hours prior to screening;
 - (2) RT-PCR or antigen positive in sample collected $>$ 72 hours but \leq 168 hours (i.e. 7 days) prior to screening, documented inability to obtain a repeat sample (e.g. due to lack of testing supplies, limited testing capacity, results taking $>$ 24 hours, etc.), AND progressive disease suggestive of ongoing SARS-CoV-2 infection.
6. Requiring oxygen by nasal cannula or by face-mask as a new treatment (or if previously on home oxygen, at a liter flow at least 2 Lpm greater than home prescription), but not on humidified heated high-flow nasal cannula (HHHFNC) at \geq 15 Lpm.
7. Can be randomized within 72 hours of initial hospital admission.
8. Agrees not to participate in another therapeutic clinical trial for the treatment of COVID-19 or SARS-CoV-2 through Day 29 without approval from the investigator(s). Taking part in other research studies, including those unrelated to SARS-CoV-2, without first discussing it with the investigators of this study may invalidate the results of this study, as well as that of the other study.

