5.2 EXCLUSION CRITERIA

An individual who meets any of the following criteria will be excluded from participation in this study:

1. Respiratory failure requiring mechanical ventilation, non-invasive ventilation including CPAP (for an indication other than previously diagnosed sleep apnea and maintained on outpatient settings), or extra-corporeal membrane oxygenation or anticipated to require any of those treatments or to die within 24 hours.
2. Anticipated discharge from the hospital or transfer to another hospital that is not a study site within 72 hours.
3. History of previous transfusion reaction.
4. Previously documented serum IgA deficiency (<7 mg/dL)
5. Documented to have received convalescent plasma in the last 60 days.

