5.3 LIFESTYLE CONSIDERATIONS

During this study, participants are asked to:

- Avoid participating in another interventional clinical trial for the treatment of SARS-CoV-2 or SARS-CoV-2. Co-enrollment for natural history studies of SARS-CoV-2 is permitted or studies unrelated to of SARS-CoV-2 can be considered if PI of both studies agree.

5.4 SCREEN FAILURES.

Following Consent and after screening evaluations have been completed, the LSI or designee will review the inclusion/exclusion criteria and determine the subject's eligibility for the study. If there is any uncertainty, the Local Site Investigator (LSI) should make the decision on whether a potential subject is eligible for study enrollment.

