6.5.1 CONCOMITANT MEDICATIONS

Use of concurrent medications is allowed if they are part of local best supportive care for SARS-CoV-2 infection.

Pretreatment with appropriate medication to minimize transfusion reactions (e.g. acetaminophen, diphenhydramine) may be given at the discretion of the local site investigator and consistent with local site's transfusion protocols.

Pre-admission level A medications will be collected by class at baseline. Concomitant medications taken for the prevention and treatment of COVID-19 in the 7 days prior to Study Day 1 (day of randomization) and concomitant medications prescribed from hospital admission through Day 28 will be collected by study site staff using the designated case report form. This information will be collected via chart review, or in person or telehealth/telephone interviews, when appropriate.

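### Section 6.5 bars convalescent plasma during the study only when it comes through an expanded access program, so non-study plasma given as ordinary care up to Day 28 breaks no stated rule

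*Combined protocol and SAP*

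**What the plan says.** Section 6.5 (Concomitant Therapy) first allows participants to be prescribed "therapy for SARS-CoV-2 that has received preliminary FDA approval whether available by prescription or under an expanded access program (EAP"), with remdesivir and dexamethasone as examples. It then makes an exception for plasma: "participants may not have previously received or be given SARS-CoV-2 convalescent plasma under the Mayo or any other EAP". Its last paragraph deals with other trials: "A participant cannot participate in another clinical trial for the treatment of SARS-CoV-2 until after Day 29". Entry to another trial after respiratory failure is allowed if the sponsor has approved an agreement between the two trials.

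The neighbouring rules are:

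- Section 5.2, exclusion 5: "Documented to have received convalescent plasma in the last 60 days".
- Section 5.1, inclusion 8: "Agrees not to participate in another therapeutic clinical trial for the treatment of COVID-19 or SARS-CoV-2 through Day 29", unless the investigators approve.
- Section 5.3: "Avoid participating in another interventional clinical trial for the treatment of SARS-CoV-2".
- Section 6.5.1: "Use of concurrent medications is allowed if they are part of local best supportive care for SARS-CoV-2 infection". Medications prescribed from admission through Day 28 are collected on a case report form.

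On use outside the trial, section 2.1 says "Convalescent plasma therapy is being used empirically" and describes plasma as readily available. Section 2.2 describes it as widely used.

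The primary analysis is by intention to treat. For secondary outcomes, Analysis of the Secondary Endpoint(s) (9.4.3 in the contents, printed as 2.4.3) recognises that joining another SARS-CoV-2 trial after respiratory failure may affect interpretation. It gives examples of sensitivity analyses, and non-study plasma is not among them.

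**The concern.** The trial compares plasma with saline, so the one treatment that the control arm must not receive is plasma. Section 6.5 recognises two routes to a SARS-CoV-2 therapy, prescription and expanded access, but its bar on plasma names only the second.

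Two consequences follow if non-study plasma is given:

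- **Before a primary event.** A saline participant would be treated with the experimental product. If plasma works, the control event rate falls, the intention-to-treat difference shrinks and power drops.
- **After respiratory failure.** The primary endpoint has already occurred and cannot change. Time to recovery and 28-day mortality still could, which is the problem that the plan acknowledges for other-trial treatment.

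There is also a recording problem. Protocol Deviations (10.1.12 in the contents, printed as 3.1.11) defines a deviation as noncompliance. Plasma that breaks no written rule would not clearly be logged as one.

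Randomisation and type I error are not affected.

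**Working it through.** **Does any rule close the gap?** Each rule was checked against one case: plasma that is neither study product, nor from expanded access, nor from another trial, given after randomisation.

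| Rule | Covers | Bars this case? |
|---|---|---|
| 6.5, plasma sentence | Expanded access plasma, before or during the study | No |
| 5.2, exclusion 5 | Plasma from any source, 60 days before entry | No |
| 5.1, inclusion 8; 5.3; 6.5, last paragraph | Other trials | No |
| 6.5.1 | Permits medications that are part of local supportive care | No |
| 6.5.2 (rescue medicine) | Marked not applicable | No |

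**What could it cost?**

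*Inputs from the plan (Sample Size Determination, 9.2 in the contents, printed as 2.2):* 30% events on saline, 20% on plasma, two-sided 0.05, 666 evaluable (333 per arm), stated power 85%, or 84.0% with the interim looks.

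*Assumptions, not in the documents:* c is the share of saline participants given non-study plasma before a primary event, and f is the fraction of the 10-point benefit that they gain. The saline event rate becomes

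p_C = 0.30 − 0.10 × c × f, with p_T = 0.20.

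*Formula:* power = Φ[(d − 1.96 × s0) / s1], where d = p_C − p_T, s0 = √[2p̄(1 − p̄)/333], p̄ = (p_C + p_T)/2, and s1 = √[(p_C(1 − p_C) + p_T(1 − p_T))/333].

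*Plan's own figure (c × f = 0):* d = 0.100, s0 = 0.03356, s1 = 0.03333. Then (0.100 − 0.06577)/0.03333 = 1.027, and power is 84.8%, which matches the stated 85%.

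*Illustration at c × f = 5%:* p_C = 0.295, d = 0.095, s0 = 0.03345, s1 = 0.03324. Then (0.095 − 0.06555)/0.03324 = 0.886, and power is 81.2%.

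| c × f | Saline rate | Difference (points) | Fixed-design power | Power with planned looks |
|---|---|---|---|---|
| 0 | 30.0% | 10.0 | 84.8% | 84.0% |
| 1% | 29.9% | 9.9 | 84.1% | not run |
| 2.5% | 29.75% | 9.75 | 83.1% | 82.2% |
| 5% | 29.5% | 9.5 | 81.2% | 80.3% |

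The last column is from simulation with looks at 222, 444 and 666 participants, the plan's efficacy boundaries of 2.947 and 2.401, and a final boundary of 2.030 solved from the remaining one-sided 0.025. Stopping is for efficacy only. The first row reproduces the plan's 84.0%.

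*80% threshold:* fixed-design power reaches 80% at c × f = 6.6%. With full benefit (f = 1) that is 0.066 × 333 ≈ 22 saline participants. The 5% case is 0.05 × 333 ≈ 17.

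*Sample size equivalent:* at 29.5% against 20%, 367 per arm (734 in total) restores 84.8%, compared with 666.

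**The case against.** **The sentence was probably meant as a general ban.** It opens as an exception to the permission just before it, and many sites would read it as covering all non-study plasma. This is likely right about intent. It does not change the words, and exclusion 5 shows that the authors used source-neutral wording elsewhere.

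**No supply route is shown.** Harm needs plasma from outside the study, expanded access and other trials, and the documents name no such source. They say that plasma is used empirically, widely used and readily available, but not through what channel. This stands, and it is why zero is a realistic value for c.

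**Safeguards exist.** The treating provider's permission is obtained before consent is sought, medications through Day 28 are collected partly by chart review, and the DMC monitors adherence. These make receipt rarer and easier to see. They do not make it a breach, and plasma is not named on the collection list.

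**The analysis plan is not closed.** The sensitivity analyses are given as examples, and a separate SAP is to follow before unblinding. This is fair: non-study plasma could still be added there.

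A reader might infer three stronger things that the documents do not support:

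- *That section 6.5.1 authorises plasma as supportive care.* It speaks of medications, while section 6.4 treats the product as a blood component. The reading is arguable at most.
- *That controls would be given more of it.* Participants and prescribers are blinded, so there is no basis for saying which arm would receive more.
- *That the trial stands to lose much of its power.* A full-benefit share of 10% would give 77.2%, but nothing in the documents supports a share of that size.

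**Conclusion.** The gap is real as a matter of wording. On its literal terms, the plan lets saline participants receive the experimental product as ordinary care from randomisation to Day 28, and no analysis rule names that case. It does not show that the sponsor chose to permit crossover, or that any will happen.

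The size is unknown. The loss of fixed-design power is 0.7 points at c × f = 1% and 3.6 points at 5%, and power stays above 80% until about 6.6%. These figures rest on an assumed share and an assumed benefit, on the plan's 30% and 20% rates, and on no missing data. The point is small and precautionary. It is worth making because closing the gap costs so little.

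**What to change.** Add one sentence to section 6.5:

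*From randomisation through Day 28, participants may not be given any non-study SARS-CoV-2 convalescent plasma, whatever its source, except within another trial approved under this section after respiratory failure; section 6.5.1 does not permit it.*

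Then:

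- Record any receipt, with date and volume, on the existing concomitant-medication form and as a protocol deviation.
- Keep the participant in the intention-to-treat analysis.
- Add non-study plasma to the sensitivity analyses described for the secondary endpoints.

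Leave the prior-receipt wording in 6.5 and exclusion 5 as they are. Section 6.5 bars earlier expanded access plasma with no time limit, while exclusion 5 covers any source for 60 days only. Relying on exclusion 5 alone would admit patients given expanded access plasma more than 60 days before. Simply deleting the expanded access phrase would bar anyone who had ever received plasma. Either would change eligibility, which this point does not require.

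The cost is amendment wording and one item on an existing form. The downside is a few more recorded deviations and the loss of a non-study plasma option for clinicians until Day 28.

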6.5.1 CONCOMITANT MEDICATIONS

Use of concurrent medications is allowed if they are part of local best supportive care for SARS-CoV-2 infection.

Pretreatment with appropriate medication to minimize transfusion reactions (e.g. acetaminophen, diphenhydramine) may be given at the discretion of the local site investigator and consistent with local site's transfusion protocols.

Pre-admission level A medications will be collected by class at baseline. Concomitant medications taken for the prevention and treatment of COVID-19 in the 7 days prior to Study Day 1 (day of randomization) and concomitant medications prescribed from hospital admission through Day 28 will be collected by study site staff using the designated case report form. This information will be collected via chart review, or in person or telehealth/telephone interviews, when appropriate.

6.5.2 RESCUE MEDICINE

Not applicable.

7 STUDY INTERVENTION DISCONTINUATION AND PARTICIPANT DISCONTINUATION/WITHDRAWAL

7.1 DISCONTINUATION OF STUDY INTERVENTION

Not applicable

7.2 PARTICIPANT DISCONTINUATION/WITHDRAWAL FROM THE STUDY

Participants are free to withdraw from full participation in the study at any time upon request, without any consequences.

If a participant requests to be withdrawn from the study, the LSI or delegatee may offer the participant an option of limited participation. The two limited participation options that may be offered are:

1. A participant can choose to withdraw from receiving study product, but agree to all other follow-up, including study staff contact and laboratory testing.

OR

2. A participant may choose to withdraw from direct participation in all study activities but allow ongoing medical records review by study staff (no contact).

A participant may also choose to withdraw completely from all study activities. If a participant fully withdraws consent, no study procedures may be performed, and no more data may be collected as of the time point at which the patient withdrew consent.

In any of the situations above, study personnel will ascertain and clearly document in the EHR any limits to ongoing participation. A participant's usual medical care is not affected by whether study participation continues (fully or to a lesser degree) or ends.

If a participant withdraws consent or is withdrawn from the study by the Local Site Investigator (LSI), an Early Termination Form will be completed. Data collected up to the point of withdrawal will be used in the analyses. If a participant agrees to limited participation the site must complete a Reduced Participation form.

